12.3.4 Hyperglycemic/Ketotic Events

Hyperglycemia is only reportable as an adverse event when any of the following criteria is met:

- The event involved DKA, as defined by the Diabetes Control and Complications Trial (DCCT)²⁴ and described below
- Evaluation or treatment was obtained at a health care provider facility for an acute event involving hyperglycemia or ketosis, or the participant contacted the site and received guidance on how to manage the hyperglycemia/ketosis
- Prolonged hyperglycemia: defined as meter BG \geq 300 mg/dL and ketones $>$ 1.0 mmol/L
- Hyperglycemia resulting in an SAE that may not otherwise meet the above criteria

Hyperglycemic events are classified as DKA²⁴ if all of the following are present:

- Symptoms such as polyuria, polydipsia, nausea, or vomiting;
- Serum ketones $>$ 1.5 mmol/L or large/moderate urine ketones;
- Either arterial blood pH $<$ 7.30 or venous pH $<$ 7.24 or serum bicarbonate $<$ 15; and
- Treatment provided in a health care facility

When a hyperglycemia/ketotic event meets the above reporting requirements, Adverse Event Form should be completed.

Events meeting DKA criteria should be considered a serious adverse event and follow the SAE reporting requirements. Hyperglycemia events not meeting criteria for DKA generally will not be considered as serious adverse events unless one of the SAE criteria above is met.

12.3.5 Relationship of Adverse Event to Investigational Device

The investigator will be responsible for making a determination on the causal relationship of the AE. Specifically, the investigator will report whether the AE was related to study procedures and/or related to the investigational device.

To ensure consistency of adverse event causality assessments, investigators should apply the following general guideline when determining whether an adverse event is related.

The causal relationship to the study procedures and the investigational device for each adverse event will be rated as follows:

- Unrelated: The event is not related to the procedures or the investigational device.
- Possibly Related: The temporal sequence is such that the relationship is not unlikely or there is no contradicting evidence that can reasonably explain the subject's condition. There is a possibility of any relation between the event and the procedures or the investigational device.
- Related: The temporal sequence is relevant or the event abates upon completion of the procedure/ investigational device, or the event cannot be reasonably explained by the subject's condition or comorbidities. The event is related or most likely associated with the procedures or the investigational device.

12.3.6 Severity (Intensity) of Adverse Events

The severity (intensity) of an adverse event will be rated on a three-point scale: (1) mild, (2) moderate, or (3) severe. A severity assessment is a clinical determination of the intensity of an event. Thus, a severe adverse event is not necessarily serious. For example, itching for several days may be rated as severe, but may not be clinically serious.

- **MILD**: Usually transient, requires no special treatment, and does not interfere with the participant's daily activities.
- **MODERATE**: Usually causes a low level of inconvenience, discomfort or concern to the participant and may interfere with daily activities but is usually ameliorated by simple therapeutic measures and participant is able to continue in study.
- **SEVERE**: Interrupts a participant's usual daily activities, causes severe discomfort, may cause discontinuation of study device, and generally requires systemic drug therapy or other treatment.

12.3.7 Outcome of Adverse Events

The outcome of each reportable adverse event will be classified by the investigator as follows:

- **RECOVERED/RESOLVED** - The participant recovered from the AE/SAE without sequelae. Record the AE/SAE stop date.
- **RECOVERED/RESOLVED WITH SEQUELAE** - The event persisted and had stabilized without further anticipated change in the event status. Record the AE/SAE stop date.
- **FATAL** - A fatal outcome is defined as the SAE that resulted in death. Only the event that was the cause of death should be reported as fatal.

- AEs/SAEs that were ongoing at the time of death; however, were not the cause of death, will be recorded as “resolved” at the time of death.
- NOT RECOVERED/NOT RESOLVED (ONGOING) - An ongoing AE/SAE is defined as the event was ongoing with an undetermined outcome.
 - An ongoing outcome will require follow-up by the site in order to determine the final outcome of the AE/SAE or until participant completes the study.
 - The outcome of an ongoing event at the time of death that was not the cause of death, will be updated and recorded as “resolved” with the date of death recorded as the stop date.
 - UNKNOWN - An unknown outcome is defined as an inability to access the participant or the participant’s records to determine the outcome (for example, a participant that was lost to follow-up).

If any UADEs are ongoing when a participant completes the study (or withdraws), the subject will continue to be followed until the event resolves or has no prospect of improvement or change, even after the participant has completed all applicable study visits/contacts, unless that subject has withdrawn their consent. For all other reportable adverse events, data collection will end at the time the participant completes the study. Note: Participants should continue to receive appropriate medical care for an adverse event after their participation in the study ends.

12.4 Reportable Device Issues

Device complaints and device malfunctions will be reported except in the following circumstances. These occurrences are expected and will not be reported on a Device Deficiency Form:

- CGM sensor, transmitter or Pod lasting fewer days than expected per manufacturer
- CGM tape or Pod adherence issues
- Battery lifespan deficiency due to inadequate charging or extensive wireless communication
- Intermittent device component disconnections/communication failures not requiring system replacement or workaround/resolution not specified in user guide/manual.
- Device issues clearly addressed in the user guide manual that do not require additional troubleshooting

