12 SAFETY

12.1 Types of Known Risks and Benefits

There are known risks and benefits. Most of the risks are not unique to the study and are typical for patients using insulin pumps, CGM, and BG meters.

The known risks are as follows:

- Hypoglycemia and/or hyperglycemia as a result of change in diet, activity, diabetes management or insulin regimen during the study.
- Hypoglycemia and/or hyperglycemia as a result of over or under delivery of insulin due to a device defect, failure or malfunction of any of the system components.
- Hypoglycemia, hyperglycemia, diabetic ketoacidosis, seizure, coma or death related to insulin administration, pump use or misuse, or Horizon™ System use or misuse.

- Use of the Pod (Omnipod® tubeless, insulin delivery pump) - Because the Pod uses only rapid-acting insulin, users are at increased risk for developing hyperglycemia if insulin delivery is interrupted. If it is untreated, prolonged hyperglycemia can quickly lead to diabetic ketoacidosis (DKA). DKA can cause symptoms such as breathing difficulties, shock, coma, or death. Further, occlusions can interrupt insulin delivery and lead to hyperglycemia or DKA. Other potential risks associated with using the Pod are:
 - Anaphylaxis (allergic shock)
 - Bruising at the Pod site
 - Bleeding at the Pod site
 - Erythema (redness at the Pod site)
 - Excoriation (raw skin at Pod site)
 - Pruritus (itching)
 - Induration (hardening of the skin at the Pod site)
 - Infection (can include heat, redness, swelling, pain, and drainage)
 - Inflammation (redness, swelling)
 - Skin reaction to adhesive at the Pod site
 - Papule (small, solid raised area on the skin similar to a pimple)
 - Pain or discomfort
 - Ulceration (skin sores)
 - Vesicles (blisters)
- Use of the CGM - risk of bruising, infection, pain and/or bleeding at the site of insertion, and skin site reaction to adhesive
- On rare occasions, the CGM sensor may break and leave a small portion of the sensor under the skin that may cause redness, swelling, or pain at the insertion site, and may require surgical removal.
- Blood sampling with fingerstick - minor discomfort and risk of infection at site of fingerstick

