An event that occurs solely due to participant (i.e., user) error in which the device functions properly generally will not be considered an ADE unless it is determined that the instructions on the screen of the device or user manual (or similar training materials) may have contributed to the event (note: the event may still meet criteria for reporting as an adverse event).

Serious Adverse Device Effect (SADE): A serious adverse device effect is defined as an adverse device effect that has resulted in any of the consequences characteristic of a serious adverse event.²⁸

Device Deficiency (DD): A device deficiency is defined as a device related complaint or malfunction or any inadequacy of a device with respect to its identity, quality, durability, reliability, safety or performance and includes misuse or use errors and inadequate labeling. A device deficiency is something that happens to a device or is related to device performance, whereas an adverse event happens to a participant. A device deficiency may occur independently from an AE, or along with an AE. An AE may occur without a device deficiency or there may be an AE related to a device deficiency.

Note: for reporting purposes, sites will not be asked to distinguish between device complaints and malfunctions.

For any event where there is suspicion that the study device is involved, the Sponsor will request that the investigator return the device for evaluation.

All device complaints or malfunctions involving any investigational component of the Omnipod Horizon™ System used in the study will be reported to the Sponsor within 5 business days of knowledge of the deficiency and documented on an appropriate eCRF. All study product associated with a reported device deficiency (PDM, Pod, and CGM) should be retained at the clinical site and returned to the Sponsor or CGM manufacturer for investigation and analysis.

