13.6.2 Evaluation of Device Deficiencies

Device deficiencies will be tabulated and listed in a manner similar to the methods described for adverse events. Any device deficiency leading to an AE or to study termination will be listed separately.

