5.5 EVALUATION OF DEVICE DEFICIENCIES

Device deficiencies will be tabulated and listed in a manner similar to the methods described for adverse events. Any device deficiency leading to an adverse event or study termination will be listed separately.

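### Protocol 12.4 keeps Pod adherence problems and short Pod life off the Device Deficiency Form even when they are suspected of causing a reportable AE, so the promised listing of deficiencies leading to an AE can be incomplete

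*Protocol*

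**What the plan says.** Protocol 12.4 (Reportable Device Issues) lists device problems that sites need not report as deficiencies: "These occurrences are expected and will not be reported on a Device Deficiency Form". The first two items are "CGM sensor, transmitter or Pod lasting fewer days than expected per manufacturer" and "CGM tape or Pod adherence issues". The other three cover battery life, intermittent disconnections and issues already handled by the user guide.

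Protocol 12.3.1 sets the general rule. It begins "All device complaints or malfunctions involving any investigational component of the" and goes on to require reporting to the sponsor within 5 business days and documentation on an eCRF. Its definition of a device deficiency is broad and takes in durability, reliability and performance. It also recognises that an AE may be related to a deficiency.

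On the analysis side, protocol 13.6.2 says: "Any device deficiency leading to an AE or to study termination will be listed separately". SAP 5.5 repeats the promise: "Any device deficiency leading to an adverse event or study termination will be listed separately". Neither names a source for the listing other than reported deficiencies.

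Protocol 12.1 explains why Pod function matters: with only rapid-acting insulin in the Pod, "users are at increased risk for developing hyperglycemia if insulin delivery is interrupted". It adds that "occlusions can interrupt insulin delivery and lead to hyperglycemia or DKA".

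**The concern.** The two analysis sections promise a complete listing of deficiencies that led to an AE. The form that would feed it is switched off for two kinds of Pod failure, whatever happened to the child. A Pod that comes loose, or ends early without an identified malfunction, stops delivering insulin, and 12.1 treats interrupted delivery as a route to hyperglycemia and, if untreated, to DKA. If an AE follows, a site that obeys 12.4 has nothing to enter on the deficiency side.

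The stake is the traceability of device-caused harm. The listing is where a reader would look to see which device failures led to events, and under 12.8 device-deficiency listings are among the compiled safety data the DSMB may receive. Any omission works in one direction: the listing can only become shorter.

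**Working it through.** No sample size, power or error rate is involved, and the plan gives no figure to reproduce. The check sets the sections side by side.

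1. **Are the two exclusions conditional?** No. The battery item is limited by cause, the disconnection item by whether the system needs replacing, and the user-guide item by whether more troubleshooting is needed. Short Pod life and adherence carry no limit. No exception for AE-linked cases appears in 12.4, elsewhere in the protocol or in the SAP.
2. **Does 12.3.1 agree?** Not as worded. It says all and does not refer to 12.4.
3. **Can the listing be filled another way?** Neither 13.6.2 nor SAP 5.5 says so. Protocol 12.2 allows the cause of a prolonged-hyperglycemia AE to be attributed to a suspected occlusion or dislodged cannula, but this is optional and tied to meter BG ≥ 300 mg/dL with ketones > 1.0 mmol/L. Section 12.3.4 makes other hyperglycemic events reportable, such as those treated at a facility or managed with site guidance, without a matching provision on cause.
4. **Is occlusion excluded?** It is not on the 12.4 list. Visits from Visit 5 onward ask about occlusion alarms as device deficiencies.

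**Scale: Pods.** From a change at least every 72 hours (protocol section 9) and Day 94 as the end of Phase 2:
- Pods per child: 94 / 3 = 31.3, a minimum
- 60 children: 60 × 31.3 ≈ 1,880
- 80 children: 80 × 31.3 ≈ 2,507

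The documents give neither the share of Pods that detach or end early nor the share of those that lead to a reportable AE. Purely as assumptions, 5–10% and 1–3% give:
- low: 1,880 × 0.05 × 0.01 = 0.94
- high: 2,507 × 0.10 × 0.03 = 7.5

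The assumed rates drive this range, so it is not an estimate.

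**Scale: DKA.** Protocol Table 5 gives 3–4% of subjects under 18 with at least one DKA and does not state the period. Expected subjects = n × q, and P(at least one) = 1 − (1 − q)^n.

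| Assumed period for p | q | Expected, n=60, p=3% | Expected, n=80, p=4% | P(at least one) |
|---|---|---|---|---|
| About the length of Phase 2 | p | 1.8 | 3.2 | 0.84–0.96 |
| One year | 1 − (1 − p)^(13/52) | 0.46 | 0.81 | 0.37–0.56 |

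On either reading only a handful of DKA cases is expected, so one missing device link would be noticeable. The table does not say how many would follow detachment or short Pod life.

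**The case against.** The strongest reply is that harm is recorded through AE reporting and does not depend on the deficiency form. DKA is a serious AE (12.3.4). Prolonged hyperglycemia is reportable, and the Pod is requested back (12.2). The Medical Monitor adjudicates every DKA, and every AE the site calls related or possibly related, for device relatedness (12.9). The DSMB is told of every DKA and severe hypoglycemia whatever the device relationship (12.6). AEs are tabulated by relationship to the device (13.6.1, SAP 5.4). No endpoint, hypothesis or success criterion uses the deficiency listing. All of this stands, and it limits the point to one descriptive listing and the deficiency data drawn from the same forms. It does not restore the link: adjudication yields relatedness, seriousness, severity, category and whether the event was anticipated, not a linked deficiency record.

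A second reply is that 12.4 is worded as an exception, so it can be read as qualifying 12.3.1. That is fair, and it makes the conflict between those two sections largely one of drafting. But on that reading the listing of any deficiency leading to an AE still cannot be complete.

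Third, a reader might infer that the whole insulin-interruption route to DKA drops out of the listing. The documents do not support that. Occlusion, the specific mechanism 12.1 names for DKA, is not excluded and is asked about at visits. Treating an occluded Pod removed early as merely short-lived is possible but strained. The user-guide item hardly fits an AE-linked case either, because the 12.2 pathway involves meter and ketone checks, Pod replacement and a call to the site.

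Last, the AE eCRF and the Safety Management Plan are not among the documents reviewed. Either may already link an AE to a device issue.

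**Conclusion.** The gap is real but narrow. Followed as written, 12.4 lets an AE caused by Pod detachment or by early Pod failure without an identified malfunction go unmatched in the listing promised by 13.6.2 and SAP 5.5. It also leaves 12.3.1 and 12.4 unreconciled. The loss is the deficiency-to-AE link, in that listing and in the deficiency data the DSMB may see.

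It would go too far to infer that such harm disappears from the record or that the DKA and severe hypoglycemia rates are understated: event capture, adjudicated relatedness and DSMB notification do not rely on the deficiency form. The number of affected cases cannot be derived from the documents; only the Pod count of roughly 1,900 to 2,500 in Phase 2 can.

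The conclusion assumes that sites apply 12.4 literally and that no form or plan outside these documents supplies the link. The change is worth making because it is cheap and expected event numbers are small.

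**What to change.** - **Protocol 12.4:** state that the exceptions do not apply when the site or the Medical Monitor suspects that the occurrence caused or contributed to a reportable AE, and that a Device Deficiency Form linked to the AE is then completed. The test should be suspected causation or contribution. A merely temporal test would call for forms on unrelated tape problems that happened to come before, for example, any emergency department visit.
- **Protocol 12.3.1:** make the requirement read as all complaints and malfunctions except as stated in 12.4.
- **13.6.2 and SAP 5.5:** no change is needed once 12.4 is amended.

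Routine early Pod changes and tape problems without such an AE stay exempt, so 12.4 keeps its purpose. No treatment rule, endpoint or sample size changes. The cost is one sentence, one cross-reference, an AE link on the deficiency eCRF if there is none yet, a few more forms and a slightly less favourable deficiency table.

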12.5 Timing of Event Reporting

SAEs possibly related or related to a study device or study procedures and UADEs must be reported to the Sponsor/CRO within 2 business days of the site becoming aware of the event. This can occur via phone or email, or by completion of the AE eCRF. If the form is not initially completed, it should be completed as soon as possible after there is sufficient information to evaluate the event. All other reportable AEs should be submitted by completion of the AE eCRF within 5 business days of the site becoming aware of the event.

Each principal investigator is responsible for reporting adverse events required by this protocol and abiding by any other reporting requirements specific to his/her Institutional Review Board or Ethics Committee.

Upon receipt of a UADE report, the Sponsor will investigate the UADE and if indicated, report the results of the investigation to all participating investigators, overseeing IRBs, and the FDA within 10 business days of the Sponsor becoming aware of the UADE per 21CFR 812.46(b). Copies of the associated reports and correspondence with the investigators, regulatory authorities, and Sponsor must be retained with study records.

The Medical Monitor must notify the DSMB of any UADEs and determine if the UADE presents an unreasonable risk to participants. If so, the Sponsor must ensure that all investigations, or parts of investigations presenting that risk, are terminated as soon as possible but no later than 5 working days after the Medical Monitor makes this determination and no later than 15 working days after first notice of the UADE.

Device deficiencies will be handled by the Sponsor or designee as described below. In the case of a Dexcom CGM transmitter or sensor device malfunction, information will be forwarded to Dexcom by the site personnel, to be handled by Dexcom's complaint management system.

If the subject is hospitalized because of or during the course of an SAE, then a copy of the hospital discharge summary must be requested for inclusion with the SAE documentation. In case of death, the investigator must make every effort to obtain a copy of the death certificate to submit to the Sponsor. When submitting copies of documentation, all subject identifying information must be redacted and only the unique subject number will be used to label the forms for identification purposes.

For any event where there is suspicion that the study device is involved, the investigator will return the device for evaluation when possible.

12.6 Safety Oversight

The study Medical Monitor will review all reportable adverse events and adverse device events that are reported during the study. SAEs will typically be reviewed within 24-hours of reporting. Other AEs will typically be reviewed approximately weekly.

A Data and Safety Monitoring Board (DSMB) will be informed of all cases of severe hypoglycemia and diabetic ketoacidosis irrespective of device relationship, all UADEs during the study and will review compiled safety data at periodic intervals. The DSMB also will be informed of any SADEs and ADEs not meeting criteria for a UADE if the Medical Monitor requests the DSMB review. The DSMB can request modifications to the study protocol or suspension or outright stoppage of the study if deemed necessary based on the totality of safety data available. Details regarding DSMB review will be documented in a separate DSMB Charter.

A safety review including 4 weeks of Phase 2 data following study recommencement from the Omnipod Horizon™ Pivotal Study will be conducted by the DSMB prior to enrollment of subjects into this study. At minimum, this will include a review of 20 pivotal subjects, with at least 3 (three) of those subjects aged 6.0-7.9 years.

12.7 Stopping Criteria

12.7.1 Participant Discontinuation of Study Participation

In the case of a UADE, the Medical Monitor will determine if the use of the study device will be suspended while the problem is diagnosed. The use of the study device may continue if the Medical Monitor believes the event is explainable, unlikely to reoccur and that it is safe for the subject to continue using the device. Alternately, the Medical Monitor may request the study subject, or all study subjects, to stop using the study device or to only use in Manual Mode. Should all study subjects be required to stop using the study device or to only use in Manual Mode due an UADE, use of the study device or Automated Mode will not be restarted until approval is received from the IRB, DSMB and FDA.

Use of the study device by a participant will be discontinued if any of the following occur:

- The investigator believes it is unsafe for the participant to continue on the intervention. This could be due to the development of a new medical condition or worsening of an existing condition; or participant behavior contrary to the indications for use of the device that imposes on the participant’s safety.
- The participant requests that the treatment be stopped
- Participant pregnancy
- One distinct episode of DKA as defined above
- One distinct severe hypoglycemia events as defined above

